The aggregate, de-identified results of this research will be presented at both national and international orthopaedic surgical meetings such as the Australian Orthopaedic Association Annual Scientific Meeting, the Australian Knee Society Meeting, and the American Academy of Orthopaedic Surgeons. We aim to have this research submitted to a high-impact medical or surgical journal for publication, and all investigators are eligible for authorship in such publications.

It is also anticipated that the results of this trial will inform future research efforts, clinical practice and surgical guidelines internationally. To that end, and to enhance transparency, reproducibility and interpretation of the study results, this protocol will be made publicly available via open-access digital publication. Additionally, the authors will publish a de-identified, participant-level data set and statistical code after journal publication to enable verification and replication of the study.

TABLES

Table 1. Adverse Events (as per ACORN Protocol)

- Drug Reaction
- Delirium
- SSI requiring oral antibiotics
- SSI requiring IV antibiotics
- SSI requiring surgery without prosthetic removal
- SSI requiring surgery with prosthetic removal
- Deep venous thrombosis
- Pulmonary Embolus
- Fat Emboli
- Respiratory Infection
- CVS
- Dislocation
- Fracture
- Nerve Injury
- Urinary Tract Infection
- Urinary Retention
- Wound Dehiscence
- Reoperation During Index Admission
- Pressure Area
- Fall
- Hypotension
- Cellulitis
- Death
- Other

Table 2. Sample Size Calculation

Parameters	Results
Power	80%
Alpha	0.05
Mean (Group 1)	30
Mean (Group 2)	15
Standard deviation	30
Sample size	125
Power (obtained)	1

Table 3. Schedule of Study Assessments

	Pre-op	Intra-op	On discharge	2 weeks	6-8 weeks	6 months	1 year	2 years
Written informed consent	X							
Demographics	X							
VERASENSE™ Data		X	X					
KOOS	X					X	X	X
FJS	X						X	X
EQ5D-5L, Satisfaction	X					X		X
Knee Range of Motion	X			X	X	X		
Radiographs	X		X			X		X
CT Perth Protocol			X					
Adverse Event Reporting		X	X	X	X	X	X	X

Table 4. SPIRIT 2013 Checklist with SPIRIT-PRO Extensions

SPIRIT 2013 Checklist with SPIRIT-PRO Extensions				
SPIRIT Section	Item No.	Item Description	SPIRIT-Pro Extension	Addressed on Page No.
Administrative Information				
Title	1	Descriptive title identifying study design, population, interventions, and if applicable, trial acronym		Title page
Trial registration	2a	Trial identifier and registry name (if not yet registered, name of intended registry)		19
	2b	All items from the World Health Organization Trial Registration Data Set		N/A
Protocol version	3	Date and version identifier		Footer
Funding	4	Sources and types of financial, material and other support		19
Roles and responsibilities	5a	Names, affiliations and roles of protocol contributors		4-5
	5b	Name and contact information for trial sponsor		19
	5c	Role of study sponsor and funders, if any, in study design; collection, management, analysis and interpretation of data; writing of the report; and the decision to submit the report for publication, including whether they will have ultimate authority over any of these activities		N/A
	5d	Composition, roles and responsibilities of the coordinating centre, steering committee, endpoint adjudication committee, data management team and other individuals or groups overseeing the trial, if applicable		N/A
Introduction				
Background and rationale	6a	Description of research question and justification for undertaking the trial, including summary of relevant studies (published and unpublished) examining benefits and harms for each intervention	Description of the PRO-specific research question and rationale for PRO assessment. Summary of PRO findings in relevant studies	6-8 14-15
	6b	Explanation for choice of comparators		8
Objectives	7	Specific objectives or hypotheses	Statement of PRO objectives or hypotheses (including relevant PRO concepts/domains)	8 14-15
Trial design	8	Description of trial design, including type of trial (e.g. parallel group, crossover, factorial, single group), allocation ratio, and framework (e.g. superiority, equivalence, non-inferiority, exploratory)		9-10
Methods: Participants, Interventions and Outcomes				
Study setting	9	Description of study settings (e.g. community clinic, academic hospital) and list of countries where data will be collected; reference to where list of study sites can be obtained		19
Eligibility criteria	10	Inclusion and exclusion criteria for participants; if applicable, eligibility for study centres and individuals who will perform the interventions (e.g. surgeons, psychotherapists)	Specify any PRO-specific eligibility criteria (e.g. language/reading requirements or pre-randomisation completion of PRO). If PROs will not be collect from the entire sample, provide rationale and describe the method for obtaining the PRO sub-sample.	10
Interventions	11a	Interventions for each group with sufficient data detail to allow replication, including how and when they will be administered		11-13
	11b	Criteria for discontinuing or modifying allocated interventions for a given trial participant (e.g. drug dose change in response to harms, participant request, or improving/worsening disease). (Stopping rules)		18

SPIRIT 2013 Checklist with SPIRIT-PRO Extensions

SPIRIT Section	Item No.	Item Description	SPIRIT-Pro Extension	Addressed on Page No.
	11c	Strategies to improve adherence to intervention protocols and any procedures for monitoring adherence (e.g. drug tablet return, laboratory tests)		16
	11d	Relevant concomitant care and interventions that are permitted or prohibited during the trial		N/A
Outcomes	12	Primary, secondary and other outcomes, including the specific measurement variable (e.g. systolic blood pressure), analysis metric (e.g. change from baseline, final value, time to event), method of aggregation (e.g. median, proportion), and time point for each outcome	Specification of the PRO concepts/domains used to evaluate the intervention (e.g. overall health-related quality of life, specific domain, specific symptom) and for each one, the analysis metric (e.g. change from baseline, final value, time to event) and the principal time point or period of interest	13-17
Participant timeline	13	Time schedule of enrolment, interventions (including any run-ins and washouts), assessments and visits for participants; a schematic diagram is highly recommended	Inclusion of a schedule of PRO assessments, providing a rationale for the time points and justifying if the initial assessment is not pre-randomisation. Specification of time windows, whether PRO collection is prior to clinical assessments and if using multiple questionnaires, whether order of administration will be standardised.	14-17 22
Sample size	14	Estimated number of participants needed to achieve study objectives and how it was determined, including clinical and statistical assumption supporting any sample size calculations	When a PRO is the primary end point, statement of the required sample size (and how it was determined) and recruitment target (accounting for expected loss to follow-up). If sample size is not established based on the PRO end point, then discuss the power of the principal PRO analyses.	17
Recruitment	15	Strategies for achieving adequate participant enrolment to reach target sample size		10
Methods: Assignment of Interventions (for Clinical Trials)				
Allocation Sequence generation	16a	Method of generating the allocation sequence (e.g. computer-generated random numbers), and list of any factors for stratification. To reduce predictability of a random sequence, details of any planned restriction (e.g. blocking) should be provided in a separate document that is unavailable to those who enrol participants or assign interventions.		10-11
Concealment mechanism	16b	Mechanism of implementing the allocation sequence (e.g. central telephone; sequentially numbered, opaque, sealed envelopes), describing any steps to conceal the sequence until interventions are assigned		11
Implementation	16c	Who will generate the allocation sequence, who will enrol participants, and who will assign participants to interventions		11
Blinding (masking)	17a	Who will be blinded after assignment to interventions (e.g. trial participants, care providers, outcome assessors, data analysts) and how		9
	17b	If blinded, circumstances under which unblinding is permissible and procedure for revealing a participant's allocated intervention during the trial		10
Methods: Data Collection, Management and Analysis				
Data Collection Methods	18a	Plans for assessment and collection of outcome, baseline and other trial data, including any related processes to promote data quality (e.g. duplicate measurements, training of assessors) and description	Justification of the PRO instrument to be used and description of domains, number of items, recall period	13-17

SPIRIT 2013 Checklist with SPIRIT-PRO Extensions

SPIRIT Section	Item No.	Item Description	SPIRIT-Pro Extension	Addressed on Page No.
		of study instruments (e.g. questionnaires, laboratory tests) along with their reliability and validity, if known. Reference to where data collection forms can be found, if not in the protocol	and instrument scaling and scoring (e.g. range and direction of scores indicating a good or poor outcome). Evidence of PRO instrument measurement properties, interpretation guidelines and patient acceptability and burden if available, ideally in the population of interest. Statement of whether the measure will be used in accordance with any user manual, and specification and justification of deviations if planned.	
	18b	Plans to promote participant retention and complete follow-up, including list of any outcome data to be collected for participants who discontinue or deviate from intervention protocols	Specification of PRO data collection management strategies for minimising avoidable missing data. Description of process of PRO assessment for participants who discontinue or deviate from the assigned intervention protocol.	16
Data management	19	Plans for data entry, coding, security and storage, including any related processes to promote data quality (e.g. double data entry, range checks for data values). Reference to where details of data management procedures can be found, if not in the protocol		20
Statistical methods	20a	Statistical methods for analysing primary and secondary outcomes. Reference to where other details of the statistical analysis plan can be found, if not in the protocol		18
	20b	Methods for any additional analyses (e.g. subgroup and adjusted analyses)		N/A
	20c	Definition of analysis population relating to protocol non-adherence (e.g. as randomised analysis) and any statistical methods to handle missing data (e.g. multiple imputation)		18
Methods: Monitoring				
Data monitoring	21a	Composition of data monitoring committee; summary of its role and reporting structure; statement of whether it is independent from the sponsor and competing interests; reference to where further details about its charter can be found, if not in the protocol. Alternatively, an explanation of why a data monitoring committee is not needed		18
	21b	Description of any interim analyses and stopping guidelines, including who will have access to these interim results and make the final decision to terminate the trial		18
Harms	22	Plans for collecting, assessing, reporting and managing solicited and spontaneously reported adverse events and other unintended effects of trial interventions or trial conduct	State whether or not PRO data will be monitored during the study to inform the clinical care of individual trial participants, and if so, how this will be managed in a standardised way. Describe how this process will be explained to participants (e.g. in the Participant Information Sheet and Consent Form)	16, 19
Auditing	23	Frequency and procedures for auditing trial conduct, if any, and whether the process will be independent from investigators and sponsor(s).		18

Ethics and Dissemination

[figure not shown]
SPIRIT 2013 Checklist with SPIRIT-PRO Extensions

SPIRIT Section	Item No.	Item Description	SPIRIT-Pro Extension	Addressed on Page No.
Research ethics approval	24	Plans for seeking research ethics committee/institutional review board approval		19
Protocol amendments	25	Plans for communicating important protocol modifications (e.g. changes to eligibility criteria, outcomes, analyses) to relevant parties (e.g. investigators, research ethics committees/institutional review boards, trial participants, trial registries, journals, regulators)		19
Consent or assent	26a	Who will obtain informed consent or assent from potential trial participants or authorised surrogates and how (see item 32)		10
	26b	Additional consent provisions for collection and use of participant data and biological specimens in ancillary studies, if applicable		N/A
Confidentiality	27	How personal information about potential and enrolled participants will be collected, shared and maintained to protect confidentiality before, during and after the trial		10, 19
Declaration of interests	28	Financial and other competing interests for principal investigators for the overall trial and each study site		19
Access to data	29	Statement of who will have access to the final trial data set and disclosure of contractual agreements that limit such access for investigators		20
Ancillary and post-trial care	30	Provisions, if any, for ancillary and post-trial care, and for compensation to those who are harmed by trial participation		19
Dissemination policy Trial results	31a	Plans for investigators and sponsor(s) to communicate trial results to participants, health care professionals, the public and other relevant groups (e.g. via publication, reporting in results databases, or other data-sharing arrangements), including any publication restrictions		20
	31b	Authorship eligibility guidelines and any intended use of professional writers		20
	31c	Plans, if any, for granting public access to the full protocol, participant-level data set, and statistical code		20
Appendices				
Informed consent materials	32	Model consent form and other related documentation given to participants and authorised surrogates		Appendix 5
Biological specimens	33	Plans for collection, laboratory evaluation and storage of biological specimens for genetic or molecular analysis in the current trial and for future use in ancillary studies, if applicable		N/A

APPENDICES

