During the enrolment period, all patients in the clinical practice of SJM and DBC for whom primary TKA is indicated will be screened for eligibility by the individual surgeon, the clinical investigators and their orthopaedic team. Once patients are found to be eligible for inclusion, they will be invited to participate. Each patient will be given a Patient Information Sheet to educate them on the purpose of the trial, its blinded nature, the confidentiality of their personal information, and requirements for participation. Participants will be given the opportunity to have an informed discussion with an operating surgeon, and their signed informed consent will be obtained prior to randomisation.

ALLOCATION

A 1:1 randomisation scheme will be generated using the computerised program at Randomisation.com (<http://www.randomisation.com>). To avoid unequal numbers of participants in each group, permuted blocks will be used, with a block size of 4 and 33 blocks allowing for randomisation of a potential 132 subjects.

One hundred thirty-two envelopes will be produced by the study coordinator prior to commencement of the study, each containing a card with the words “Kinematic Alignment” or “Mechanical Alignment” written on it. The opaque envelopes will contain the correct card according to the randomisation plan, and will be sealed and numbered consecutively on the outside. There will be no external information indicating which option is contained on the card within.

Pre-operative planning will be undertaken on each patient for both the intervention and control arms of the study. (See Pre-operative Templating below.) Immediately prior to induction of anaesthesia, a member of the surgical team will open the next envelope in the randomisation sequence from a locked box kept in theatre, and the patient will be allocated to either the intervention or control group.

Bilateral procedures will be included, and randomised once, with both sides being assigned to the same group.

SURGICAL TECHNIQUE

Pre-operative Templating

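### A fixed, printed block size of 4 at one hospital with unblinded surgeons lets a well-informed observer foresee up to one allocation in three

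*Protocol*

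**What the plan says.** The Allocation section of the protocol describes one list: "A 1:1 randomisation scheme will be generated using the computerised program at Randomisation.com", and "permuted blocks will be used, with a block size of 4 and 33 blocks allowing for randomisation of a potential 132 subjects". No stratification factor is named. The opaque envelopes "will be sealed and numbered consecutively on the outside". At surgery, "a member of the surgical team will open the next envelope in the randomisation sequence from a locked box kept in theatre"; this happens "Immediately prior to induction of anaesthesia".

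Under Study Design, two surgeons at one hospital perform every operation and are not blinded. The recruitment text after the exclusion criteria says that patients "will be screened for eligibility by the individual surgeon, the clinical investigators and their orthopaedic team", and that "their signed informed consent will be obtained prior to randomisation". Pre-operative Templating adds that the final surgical plan is recorded before randomisation. It also counts the two surgeons among the protocol's authors.

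Under Primary Outcome Measure, the 10-degree pressure difference is the mean of readings by the operating surgeon and an assistant.

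Table 4 reproduces the SPIRIT checklist. Item 16a says that "details of any planned restriction (e.g. blocking) should be provided in a separate document that is unavailable to those who enrol participants" or who assign interventions. The entry for that item points to pages 10-11 of the protocol itself.

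**The concern.** With a constant, known block size, the end of each block can be deduced from what came before. The envelopes are numbered in sequence, so the number shows the position within the block: every fourth envelope closes one. Someone who has kept count knows that arm before the envelope is opened, however opaque it is.

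The people best placed to keep count are those with discretion over who comes next. The surgeons help to screen, and the theatre team opens the envelopes. Long-leg films are measured and plans for both arms prepared before surgery, so the anatomy of each candidate is known while the next arm may also be known. If an easier or harder knee is brought forward or held back accordingly, the arms differ at baseline in a way randomisation was meant to prevent. The primary outcome is read in theatre by the unblinded surgeon and the assistant, so blinding of later assessors gives it no protection.

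**Working it through.** **Inputs.** Allocation ratio 1:1, block size 4, 33 blocks (Allocation); two surgeons, one hospital (Study Design). The split of cases between the surgeons is not stated; a share of 50% to 80% for one surgeon is assumed.

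**The plan's own figure.** 33 × 4 = 132, as stated.

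**Observer who knows every earlier allocation in the block.** A block with two of each arm has 6 equally likely orders. An allocation is certain once one arm is used up within the block.

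| Position in block | Probability that it is certain | Best-guess accuracy |
|---|---|---|
| 1 | 0 | 1/2 |
| 2 | 0 | 2/3 |
| 3 | 1/3 (first two alike) | 2/3 |
| 4 | 1 | 1 |

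- Certain: (0 + 0 + 1/3 + 1)/4 = 1/3, so 132 × 1/3 = 44 on average.
- Best guess: (1/2 + 2/3 + 2/3 + 1)/4 = 17/24 = 70.8%, against 50% under simple randomisation.
- If enrolment stops at the sample size of 125, there are 31 full blocks and one further patient: 31 × 4/3 = 41.3 certain, or 33.1%.

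**Surgeon who knows only his or her own cases, plus the envelope number.** Let p be that surgeon's share, with cases falling independently.

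- Position 3 is certain if positions 1 and 2 were both own cases and alike: p²/3.
- Position 4 is certain if all three earlier cases were own, p³, or if exactly two were own and alike, 3p²(1 − p) × 1/3 = p²(1 − p). The sum is p².
- Average over four positions: (p²/3 + p²)/4 = p²/3.
- p = 0.5 gives 0.25/3 = 8.3%; p = 0.8 gives 0.64/3 = 21.3%; p = 1 returns 33.3%.
- Best-guess accuracy for this observer, by enumeration, is 59.9% at p = 0.5 and 65.7% at p = 0.8.

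**Alternatives, for an observer who knows every earlier allocation and the possible sizes.** Fixed blocks were enumerated. Random sizes were simulated (1,500 lists of 132), with the observer updating by Bayes' rule.

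| Scheme | Certain | Best guess |
|---|---|---|
| Fixed 4 (protocol) | 33.3% | 70.8% |
| Fixed 6 | 25.0% | 68.3% |
| Fixed 8 | 20.0% | 66.6% |
| Random 4 or 6 | about 5.5% | about 69.2% |
| Random 4, 6 or 8 | about 2.3% | about 68.0% |

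A larger fixed block helps little. Random variation removes most of the certainty but only a small part of the guessing advantage.

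**The case against.** The strongest reply is that the procedure already closes the usual doors. All primary knee replacement patients in both practices are to be screened. Consent is signed and the surgical plan recorded before allocation, and the envelope is opened only just before induction. A patient's place in the sequence follows the order of surgery, not of consent, so the moment of consent does not set the arm. A certain position becomes known only once the preceding envelopes have been opened, often after the next patient has been booked. All of this stands, and it narrows the opening to invitation and theatre order. It does not remove foreknowledge, because a predictable envelope need not be opened to be known.

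Several stronger readings are tempting but lack support:

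- **That each surgeon can foresee one allocation in three.** That needs knowledge of the other surgeon's cases. One hospital and one shared box make this plausible, but the protocol does not say it.
- **That lack of stratification causes the predictability.** It does not. A shared list dilutes what one surgeon can infer, and separate fixed-block lists would give each surgeon the full one third from own cases alone.
- **That the surgeons take consent.** The protocol offers patients a discussion with an operating surgeon but does not say who obtains consent.
- **That concealment is defeated and the result biased.** The documents show an opportunity and give nothing from which to estimate a bias.
- **That the protocol contradicts itself on item 16a.** The wording is the checklist's general description of the item, not a commitment by this trial. The protocol departs from a standard that it reproduces and marks as addressed.

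**Conclusion.** The concern holds as a moderate, avoidable weakness in allocation concealment. The share of allocations known with certainty runs from 8.3%, for a surgeon who sees only own cases at an equal split, to 33.3%, for someone who follows every case. Both figures assume that the observer knows the block size, which is printed, and reads the envelope number. The own-case range also rests on the assumed 50% to 80% share. The existing safeguards limit use of this knowledge to invitation and theatre order. The finding is a risk of selection on an outcome read by unblinded staff; whether any selection occurs cannot be judged from the protocol.

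**What to change.** Regenerate the unopened envelopes with randomly varied block sizes, for example 4, 6 and 8. Record the sizes in a separate document unavailable to screening and operating staff, and delete the block size from the protocol text. Item 16a in Table 4 can then refer to that document.

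A reader might expect hidden random sizes to make every allocation uncertain. That fails if the set of sizes becomes known: about 2.3% would still be certain. The gain is the loss of near-certainty, not of all guessing. Separate lists per surgeon and a surgeon term in the analysis are not needed for this repair; the Data Analysis section names only a t-test for comparing means of continuous variables.

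The cost is the administrative work of regenerating and resealing envelopes, and a slightly larger possible imbalance at the end. The largest imbalance at any moment is half the current block: 2 patients with blocks of 4, and up to 4 with blocks of 8.

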Two knee arthroplasty surgeons (SJM, DBC) at one hospital will perform all surgeries. Each surgeon will assess compartmental loads at three positions of knee flexion, verified by navigation data, and these measures will be repeated by the surgical assistant to ensure inter-observer reliability and consistency. The surgical technique described in Appendix 2 and 3. Data will be collected on the frequency and degree of any further adjustments required to satisfactorily balance the knee, as well as the final balance achieved. Although the surgeons will not be blinded to the allocation, the participants, assessors and statisticians will be blinded to enable unbiased collection of patient-reported outcomes and functional outcomes as secondary outcome measures.

To maintain the integrity of the trial, unblinding will occur only when knowledge of the alignment allocation is essential for further clinical management of the patient. Because both treatment arms offer current, routine standards of care, we do not anticipate this need will eventuate. If necessary however, the investigator will contact

the study coordinator to obtain the allocation assignment, and the code break will be reported in the context of Complications documentation.

Inclusion criteria

1. Patients who meet the indications for primary unilateral or bilateral total knee arthroplasty using the Smith & Nephew Legion™ posterior-stabilised total knee arthroplasty system.
2. Patients diagnosed with one or more of the following conditions:
 - Osteoarthritis
 - Rheumatoid inflammatory arthritis
 - Post-traumatic osteoarthritis

Exclusion criteria

1. Revision TKA
2. Previous insufficiency fracture
3. Prior Grade 3 ligamentous knee injury to posterolateral corner (PLC) or lateral collateral ligament (LCL). Grade 3 medial collateral ligament (MCL) injuries treated conservatively may be included so long as they were deemed by the surgeon to have healed with a maximum of Grade 1 laxity.
4. Prior femoral, tibial or patellofemoral osteotomies
5. Ipsilateral foot/ankle or hip arthritis
6. Patients who are unable to provide consent or fulfil the study requirements due to cognitive incapacity or English-language deficiency

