either 86 to 93 degrees, depending on which end of the safe zone is closer. If the pre-operative plan requires LDFA and MPTA resections that would lead to a HKA greater than 4 degrees, then the LDFA and MPTA will be adjusted so the total HKA does not exceed the safe zone threshold. In order to reduce the risk of implant subsidence or loosening in the presence of osteoporotic bone, patients with a documented history of osteoporosis requiring bone anti-resorptive therapies, patients with documented insufficiency fractures or patients greater than 80 years of age will have the resection angle range for LDFA and MPTA narrowed to 87 to 93 degrees.

A web-based calculator has been designed to assist with these calculations to reduce any potential error. Most surgical instrumentation, including the navigation system used for this study, measure distal femoral and proximal cuts as either 'varus' or 'valgus'. For the LDFA, 90 degrees is neutral, 86 degrees is 4 degrees of valgus and 93 degrees represents 3 degrees of varus. To avoid errors at the time of surgery, it the varus/valgus figures that correspond to the surgical navigation data that are produced and recorded in the surgical plan. The final surgical plan will be recorded prior to randomisation.

Surgical Technique

Following randomisation, the patients will be allocated to either the intervention group or the control group. All procedures will be performed using optical navigation (OrthoMap Precision Navigation, Stryker, Kalamazoo, MI, USA). The distal femoral and proximal tibial resection will be made as per the allocated group. Femoral component rotation will be set in the KA group parallel to the native posterior condylar axis and in the MA group parallel to the surgical transepicondylar axis. In the KA group, if the planned tibial cut angle has been reduced in order to fall within the safe zone, then the femoral component will be externally rotated by the same amount that the tibial cut was reduced in order to rebalance the flexion gap. A secondary check of flexion gap symmetry will also be undertaken using a gap tensiometer.

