Trial components will then be inserted prior to any soft tissue release (other than those required by a standard approach). During trialling, the surgeon will determine the most suitable size of tibial insert, and this will be replaced by a VERASENSE™ insert of the same size. The extensor mechanism will be approximated using a towel clip, and the knee cycled through a full range of movement. Occasionally it may be necessary to change the thickness of the VERASENSE™ insert in response to the pressures being either too high or too low. In this case, the data recordings will be repeated, and the new values will replace those recorded initially. Assessment of knee extension with the computer navigation system will be performed concurrently to ensure that an extension loss of no more than 5 degrees is apparent.

Following this, the surgeon will support the posterior thigh with one hand and rest the heel in the other to reduce the amount of varus and valgus stress placed on the knee (Appendix 1). The knee will then be flexed to 90 degrees (using the optical navigation

to quantify the flexion) and the pressure values captured in this position. This will be repeated at 45 degrees and 10 degrees. The readings will be recorded on the study data collection form by a non-operative member of the surgical team. These steps will be repeated by the surgical assistant, and the data recorded for a second time.

The surgeon will then undertake final balancing of the total knee replacement by standard operating techniques using the Verasense™ insert (Appendices 2 and 3). Any soft tissue or bony adjustments undertaken to achieve this will be recorded on the data collection form. Once knee balancing has been performed, the pressure data will be recorded again.

INTERVENTIONS

Intervention (KA) Group

In the KA group, the surgeon will perform the initial bony resections according to the surgical plan that was defined prior to randomisation. This plan will include an aim for femoral and tibial component position relative to the mechanical axis of the bones. These resections will be guided and validated by the computer navigation system to ensure maximum accuracy. The rest of the procedure will be completed as per the surgical technique described above.

Control (MA) Group

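### The allocation envelope is opened before induction, earlier than any described step needs the arm: an avoidable risk to patient blinding and to the approach that precedes the primary reading

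*Protocol*

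**What the plan says.** The Allocation section of the protocol fixes when the arm becomes known: "Immediately prior to induction of anaesthesia, a member of the surgical team will open the next envelope in the randomisation sequence". The envelope comes "from a locked box kept in theatre, and the patient will be allocated to either the intervention or control group". Envelopes are opaque, sealed and numbered, "each containing a card with the words “Kinematic Alignment” or “Mechanical Alignment” written on it".

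The same section says "Pre-operative planning will be undertaken on each patient for both the intervention and control arms of the study", and Pre-operative Templating adds: "The final surgical plan will be recorded prior to randomisation". Under Surgical Technique, the first step tied to the allocated group is the distal femoral and proximal tibial resection.

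On blinding, Study Design states: "Although the surgeons will not be blinded to the allocation, the participants, assessors and statisticians will be blinded". The reason given is unbiased collection of patient-reported and functional outcomes.

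On soft tissue before the primary reading, Surgical Technique says: "Trial components will then be inserted prior to any soft tissue release (other than those required by a standard approach"). Data Analysis places the primary reading after the bone cuts and before soft-tissue correction, as the mean of the surgeon's and the assistant's values.

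**The concern.** The protocol reveals the arm in theatre at a point when the patient is not yet anaesthetised and no incision has been made. Nothing in the text explains why it is needed then. Three things are at stake.

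- **The patient blind.** KOOS, FJS-12, EQ5D-5L and the satisfaction questions are all self-reported over follow-up, and KOOS has its own power calculation. The card names the arm in plain words. Patients have been told the purpose of the trial and offered a discussion with a surgeon, so a card seen or overheard would mean something to them. No step is described for keeping it from them.
- **The primary outcome.** The initial 10-degree delta is meant to show what the cuts achieve before any balancing. The releases of the standard approach come before it and are made by a surgeon who already knows the arm. The manufacturer's quick-reference guide in the appendices treats medial and lateral release as a way to change compartment loads, so the approach could in principle move the endpoint.
- **Loss after allocation.** A case abandoned or changed between envelope and first cut has a known arm and no primary reading, whereas the protocol expects no loss for that variable.

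**Working it through.** **Order of steps, from the protocol**

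1. Both plans are prepared and the final plan is recorded (Allocation; Pre-operative Templating).
2. The envelope is opened in theatre (Allocation).
3. Anaesthesia is induced.
4. The standard approach is made, with whatever releases it requires (Surgical Technique).
5. Arm-specific resections and femoral rotation follow, with a tensiometer check of the flexion gap.
6. Trial components are placed and the insert size chosen. The insert thickness may be changed, in which case new readings replace the first.
7. The primary reading is taken by surgeon and assistant.

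The arm is first used at step 5 and is known from step 2. Steps 3 and 4 are therefore exposed without a stated need. Moving the opening to just before step 5 would cover both. It would not touch steps 5 to 7, because the surgeon must know the arm in order to cut.

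**The protocol's own sample size, as a check on the inputs**

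Inputs from Sample Size: difference 15 psi, SD 30 psi, 5% significance, 80% power, 1:1 allocation. Sidedness is not stated, so two-sided is assumed.

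Total n = 4 × [30 × (1.960 + 0.842) / 15]² = 125.6, or 63 per arm and 126 in total. The protocol states 125, so the figure reproduces to within rounding.

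**Illustration of what a shift would do**

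The documents give no figure for the effect of approach releases, so the shift b is an assumption.

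Standard error of the difference = 30 × √(2 / 62.5) = 5.37.

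Two-sided type I error with no true difference = Φ(−1.96 + b/SE) + Φ(−1.96 − b/SE). Power if the shift works against the kinematic arm is computed with a difference of 15 − b.

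| Assumed shift b (psi) | b/SE | Two-sided type I error | Power at a true difference of 15 |
|---|---|---|---|
| 0 | 0 | 5.0% | 79.8% |
| 2 | 0.37 | 6.6% | 67.8% |
| 3 | 0.56 | 8.6% | 60.9% |
| 5 | 0.93 | 15.4% | 46.2% |

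A shift of 5 is one third of the 15 psi target difference (5/15 = 0.33), which is a lot to ascribe to the approach alone. The table shows how sensitive the test is. It does not estimate a bias.

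**The case against.** The strongest reply is that the text contains no error or contradiction. Surgeon unblinding is declared openly. The envelope is already opened late, after consent and after the plan is recorded, so the larger danger, a plan altered once the arm is known, has been removed. All of that stands, and it makes this a matter of refinement.

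Two stronger readings are tempting, and the documents do not support either.

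- **That patients are unblinded.** A reader might infer this from the timing. The protocol only has one team member open an opaque envelope; nothing says the card is shown or read out. Disclosure is a risk and not a described event. Timing alone does not secure the blind either: keeping the card from the patient matters whenever it is opened.
- **That all soft-tissue handling before the primary reading is avoidably exposed, or that the primary result is biased.** Only the approach releases could be masked, and the protocol limits these to what a standard approach requires. Femoral rotation, insert choice, thickness change and the readings follow the arm-specific cuts.

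It is also fair to say that the approach is barely described, so the claim that nothing needs the arm earlier rests partly on silence. A practical reason such as theatre set-up is possible, though none is stated.

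The point about loss after allocation is small: the window from induction to first cut is short, and the primary analysis is by intention to treat.

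What remains is that the protocol gives no reason for opening before induction, that both plans are ready, and that the exposure can be avoided at almost no cost. Surgeon unblinding cannot be avoided from the first cut onward, but that does not justify it during the approach.

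**Conclusion.** The point holds as a minor, easily avoided weakness in conduct. The envelope is opened earlier than any described step requires. This puts the promised patient blind at avoidable risk, lets the approach releases be made with knowledge of the arm before the primary reading, and slightly lengthens the window for loss after allocation.

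Its size is unknown. The rise in type I error to between about 6.6% and 15% follows only if the approach shifts the delta by an assumed 2 to 5 psi, with SD 30 and 125 patients. Nothing in the protocol anchors such a shift, so these figures should not be cited as the trial's error rate. The sample size is not affected.

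The conclusion assumes that a patient not yet induced may be able to see or hear what happens in theatre, and that no undescribed step needs the arm before the resections. Priority is low to moderate.

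**What to change.** Amend the Allocation section so that the envelope is opened after induction and after exposure of the knee (the first knee in a bilateral case), immediately before the first bone resection. A team member already present should open it. Add that the card is neither shown nor spoken aloud where the patient could see or hear it. The plans for both arms stay to hand, as they already do.

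State that in bilateral cases this masks only the first knee's approach. Both sides share one allocation, so the arm is known once the first knee has been cut.

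If there is a practical reason for opening earlier, the protocol should give it and say how the card is kept from the patient.

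The cost is a sentence or two in the protocol, a brief pause during the case, and theatre set-up that allows for either arm. No patients, staff or procedures are added. The steps from the resections onward remain unblinded, and the amendment should not claim otherwise.
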